The EPI-MAL-002 study started in Q4 2015 and will last for approximately 5 years (depending on recruitment timelines). EPI-MAL-003 *started in Q1 2019* when the vaccine *became* available in the study sites that are exposed clusters after its implementation according to WHO guidelines in the framework of the MVIP (first vaccine introduction *was* foreseen in 2018, see section 9.2).

(Amended 5 May 2020)

In parallel with both EPI-MAL-002 and EPI-MAL-003, a third study (EPI-MAL-005) is conducted to measure malaria transmission intensity (MTI) and other malaria control interventions at community level in the study site areas. This study began in Q4 2014, at the first malaria transmission peak season in the West African sites with peak malaria transmission in the second half of the year, and will run through the completion of EPI-MAL-003. It is taking place in similar if not identical settings as EPI-MAL-002 and EPI-MAL-003.

Finally, describing the overall morbidity and mortality in this population is thought to have broader utility beyond these malaria studies, and could serve as baseline data for other disease control and prevention studies.

CONFIDENTIAL115055 (EPI-MALARIA-002 VS AME)
Protocol Amendment 7 Final**8. RESEARCH QUESTION AND OBJECTIVES****8.1. Co-primary objectives**

- To estimate the incidence of AESI², and of other AE leading to hospitalisation or death, in children, prior to implementation of RTS,S/AS01_E.
- To estimate the incidence of aetiology-confirmed meningitis, in children, prior to implementation of RTS,S/AS01_E.

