Note: There might be an overlap of studies EPI-MAL-002 and EPI-MAL-003. Therefore, children enrolled in active surveillance of EPI-MAL-002 and who meet the eligibility criteria for the EPI-MAL-003 study may have their study conclusion for the EPI-MAL-002 study before the end of the 44 months of active follow-up if enrolled in EPI-MAL-003 (see Section 9.2.7.1.12).

[figure not shown]
Enhanced hospitalisation surveillance:

All children under the age of 5 years of age, within the study areas, not already enrolled in the active surveillance (because parents/ LARs declined enrolment in active surveillance or because recruitment had been completed) or not eligible for active surveillance, are eligible for enrolment in enhanced hospitalisation surveillance during any hospitalisations throughout the whole study period, to allow data collection regarding those hospitalisations (see [Figure 1](#) and Section 9.2.7.2). For the purpose of this study, hospitalisation is defined as spending at least one night at a health care facility.

In this protocol, active surveillance will refer to children who are enrolled in active surveillance, and enhanced hospitalisation surveillance will refer to children who are enrolled in enhanced hospitalisation surveillance. Data collected regarding the hospitalisation will be uniformly collected whether the child is enrolled in active surveillance or in enhanced hospitalisation surveillance.

Because of a possible overlap of studies EPI-MAL-002 and EPI-MAL-003, study conclusion of EPI-MAL-002 for children enrolled in enhanced hospitalisation surveillance will be done at start of study EPI-MAL-003 (as the RTS,S/AS01_E vaccine becomes available in the sites that are exposed clusters).

CONFIDENTIAL

115055 (EPI-MALARIA-002 VS AME)
Protocol Amendment 7 Final**Figure 1** Study design overview

* Hospitalisation is defined as spending at least one night at a health care facility

V = visit; W = week(s); M = month(s); SC = study conclusion (i.e. study end or child reaches 5 years of age, whichever occurs first); Enrol = enrolment.

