All malaria events (morbidity, mortality and hospitalisation) will be monitored throughout the study. Background incidence rates of any malaria and severe malaria, including cerebral malaria, will be collected. This will enable the investigation of the impact (indirect, total and overall effect) of the RTS,S/AS01_E vaccine by comparing all malaria events in EPI-MAL-002 to all malaria events in unvaccinated children in EPI-MAL-003 (indirect effect), in vaccinated children in EPI-MAL-003 (total effect), or in all children in EPI-MAL-003 (overall effect); for children enrolled in the active surveillance. The mortality rate, overall and by gender, will also be estimated.

Since RTS,S/AS01_E is only protecting against *P. falciparum*, all analyses done for any malaria cases and for severe malaria cases regardless of the plasmodium species will be repeated for episodes with evidence of the *P. falciparum* parasite only. Analyses will also be performed for cerebral malaria due to *P. falciparum*, which is a complication of severe *P. falciparum* malaria (see Section 9.2.5.5 for case definitions).

CONFIDENTIAL115055 (EPI-MALARIA-002 VS AME)
Protocol Amendment 7 Final***Active surveillance***

In order to detect the events of interest, active surveillance will be conducted among enrolled subjects through a series of home based visits and continuous monitoring of outpatient visits and hospitalisations at all health care facilities. For children in the 6-12 weeks group (identified at the first administration of DTP/HepB/Hib vaccine) these home visits will take place approximately 1 week after administration of each dose of DTP/HepB/Hib vaccine (V1, V2, V3), and 6 weeks (V4), 6 months (V5) and 18 months (V6) after administration of the last dose of DTP/HepB/Hib vaccine, followed by visits approximately 5 weeks (V7), 12 months (V8) and 24 months (V9) after V6, to mimic the potential active follow-up in study EPI-MAL-003 ([Figure 1](#)).

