In the event of death occurring at home, the cause of death will be systematically obtained through verbal autopsy using the INDEPTH Standard Verbal Autopsy Questionnaire [[INDEPTH](#), 2003] as is routinely done in the study area.

If a site is not part of the INDEPTH network, or does not have an equivalent surveillance system in place, the INDEPTH procedures for verbal autopsy might be implemented to ensure consistency across study sites.

CONFIDENTIAL115055 (EPI-MALARIA-002 VS AME)
Protocol Amendment 7 Final**9.2.7.1.12. Study conclusion**

Subjects will exit the study when they reach 5 years of age or at study end (whichever occurs first), if not earlier due to migration or in the event of death.

At the study conclusion (home visit, V10), a record will be taken of the subject's health and vital status, any disabilities and all vaccinations received.

The investigator will review collected data to ensure accuracy and completeness and will complete the Study Conclusion screen in the eCRF.

Note: There might be an overlap of studies EPI-MAL-002 and EPI-MAL-003. Children enrolled in active surveillance of EPI-MAL-002, and not eligible for RTS,S/AS01_E vaccination or declining vaccination will continue to be followed up to the study conclusion visit in EPI-MAL-002. Children enrolled in active surveillance of EPI-MAL-002, and becoming vaccinated with RTS,S/AS01_E will have their study conclusion of EPI-MAL-002. Thereafter, these children can be eligible and enrolled in EPI-MAL-003 according to the inclusion/ exclusion criteria and the EPI-MAL-003 recruitment procedures. For children enrolled in enhanced hospitalisation surveillance of EPI-MAL-002, study conclusion of EPI-MAL-002 will be done at start of study EPI-MAL-003 (as the vaccine becomes available in the study sites that are exposed clusters). Thereafter, these children can be eligible and enrolled in active surveillance or in enhanced hospitalisation surveillance of EPI-MAL-003 according to the inclusion/ exclusion criteria and the EPI-MAL-003 recruitment procedures.

CONFIDENTIAL

115055 (EPI-MALARIA-002 VS AME)
Protocol Amendment 7 Final

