#### **3.2. Secondary Objectives**

In children living in the study area, prior to implementation of RTS,S/AS01E:

- To estimate the incidence of aetiology confirmed, and/or probable meningitis (final classification).
- To estimate the incidence of probable meningitis (final classification).
- To estimate the incidence of aetiology confirmed, probable and/or clinically suspected meningitis (final classification).
- To monitor trends over time of meningitis cases identified at site level (first line laboratory).
- To describe risk factors for AESI, other AE leading to hospitalisation or death, meningitis and malaria.
- To describe the causes of hospitalisation (including AESI, other AE, meningitis and malaria).
- To describe the causes of death, overall and by gender.
- To assess the risk of febrile convulsions during the 7-day period and 1-month period following administration of routine EPI vaccines.

---

 Acute disseminated encephalomyelitis (ADEM), encephalitis, Guillain-Barre Syndrome, hypotonic hypo responsive episode (HHE), general convulsive seizure  
Intussusception, hepatic failure or renal insufficiency  
Juvenile chronic arthritis, Stevens-Johnson syndrome/toxic epidermal necrolysis, Henoch-Schonlein purpura, Kawasaki disease  
Diabetes mellitus type I, thrombocytopenia, anaphylaxis

- To estimate the incidence of any malaria (including *P. falciparum* malaria) diagnosed by rapid diagnostic test (RDT) and/or microscopy.
- To estimate the incidence of severe malaria (including *P. falciparum* malaria) diagnosed by RDT and/or microscopy.
- To estimate the incidence of cerebral malaria (malaria diagnosed by RDT and/or microscopy).
- To estimate the prevalence of anaemia among hospitalised children.
- To estimate the incidence of all-cause hospitalisations and hospitalisations attributed to malaria (including *P. falciparum*).
- To estimate the mortality rate (all-cause mortality and deaths attributed to malaria [including *P. falciparum*]), overall and by gender.

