#### Management of first year of inclusion:

During the first year of inclusion (i.e. 2016), recruitment was done according to Protocol Amendment 3 where children had to be less than 3 years old with a corresponding census. As a consequence, IR in children < 5 years will be computed after the application on field of the Protocol Amendment 4:

- *Kintampo: 12 June 2017 in AS and 22 May 2017 in EHS*
- *Kombewa: 9 March 2017*
- *Navrongo: subjects entered directly under protocol amendment 4 (25 September 2017)*

The method to compute incidence will be described in a technical annex of the specific Mock TFL for the final analysis.

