### 7.2.13. Last contact date

The last contact date will be derived as:

- For deceased subjects the last contact date will be set as the death date.
- For subjects who have finished their participation in the study and for whom their participation did not finish prematurely (i.e. “Did the study participant finish its participation in the study prematurely” equal No) the last contact date will be set as the last contact date from study conclusion CRF page
- For the other subjects (i.e. “Did the study participant finish its participation in the study prematurely” not equal No) the last contact date will be defined as the latest date among:
  - Date of consent
  - Date of reconsent
  - Last date of hospitalisation
  - Last discharge date of hospitalisation
  - Last check-up after discharge
  - Last date of outpatient visit
  - Last home visit
  - Date of enrollment of EPI-MAL-003 study
  - ***Date of RTS,S/AS01E vaccine***
  - Date of migration (From Study continuation or from Study conclusion)

Notes:

- The last contact date recorded in study conclusion CRF page will not be used for this scenario (i.e. when “Did the study participant finish its participation in the study prematurely” not equal No).
- The last contact date will not be computed using start and end date of symptoms associated with events

In addition:

- For subjects enrolled with protocol amendment 4 or subjects enrolled with protocol amendment 3 and who signed the ICF addendum related to protocol amendment 4, the last contact date should not be after the child reaches 5 years ***or 44 months follow-up after visit 1 of the last child enrolled in AS per site whichever comes first:***
  - ***Kombewa: 7 April 2022***
  - ***Kintampo: 27 April 2022***
  - ***Navrongo: 19 July 2022***

- For subjects enrolled with protocol amendment 3 who did not sign the ICF addendum related to protocol amendment 4 (meaning that the reason for not signing the addendum is different than “Study participant enters directly with Protocol Amendment 4”), the last contact date should not be after the child reaches 3 years or 24 months follow-up per site whichever comes first:
  - Kombewa: 25 January 2018*
  - Kintampo: 7 February 2018*
  - Navrongo started directly under protocol amendment 4*

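### Active-surveillance person-time runs past vaccine introduction with no stop or split, so the dose-4, Month 32 and Month 44 rates (and, at Navrongo, D3 to D3+1Y) are not purely pre-implementation incidence

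*SAP*

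**What the plan says.** **Objective.** Protocol 8.1 sets the co-primary aim "To estimate the incidence of aetiology-confirmed meningitis, in children, prior to implementation of RTS,S/AS01_E", with matching wording for AESI and other AE. The secondary objectives in SAP 3.2 open "In children living in the study area, prior to implementation of" RTS,S/AS01E.

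**Introduction.** Protocol 7.4 dates the start of EPI-MAL-003 to Q1 2019 and ties it to the vaccine being "available in the study sites that are exposed clusters after its implementation according to WHO guidelines in the framework of the MVIP". Protocol 9.2 expects the Ghana and Kenya sites to be those exposed clusters. SAP 6.1 keeps only Kombewa, Kintampo and Navrongo in the analysis.

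**Enhanced hospitalisation surveillance (EHS).** It ends at that boundary: "study conclusion of EPI-MAL-002 for children enrolled in enhanced hospitalisation surveillance will be done at start of study EPI-MAL-003" (Protocol 9.1).

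**Active surveillance (AS).** It does not. Under Protocol 9.2.7.1.12, vaccinated children conclude the study, while those ineligible for RTS,S/AS01E "vaccination or declining vaccination will continue to be followed up to the study conclusion visit in EPI-MAL-002". SAP 7.2.13 limits last contact to age 5 or "44 months follow-up after visit 1 of the last child enrolled in AS per site whichever comes first". The resulting dates are 7 April 2022 (Kombewa), 27 April 2022 (Kintampo) and 19 July 2022 (Navrongo). The stopping events in SAP Tables 2 and 3 are individual ones (event, death, next dose, end of window, last contact, migration, age 5) or the end of the study. None is the date of introduction at the site.

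**Use.** Protocol 9.1.1 intends vaccine impact to be assessed "by comparing all malaria events in EPI-MAL-002 to all malaria events in unvaccinated children in EPI-MAL-003 (indirect effect"), with total and overall effects built on the same baseline.

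**The concern.** After introduction, an unvaccinated child in an exposed cluster no longer contributes pre-implementation experience. Three things can differ: calendar period, possible indirect protection against malaria, and who remains, since vaccinated children leave. None of these is direct vaccine exposure.

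Pooling this time into the AS rates gives a quantity other than the one the objective names. For malaria outcomes, if an indirect effect exists, the baseline already contains part of it, so a later before/after contrast moves towards the null. The sites also differ greatly in how much of their follow-up falls after introduction, so site comparisons partly compare calendar periods.

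The only AS/EHS incidence reported by calendar year is the under-5 community rate (SAP 6.9.3.3). Neither Protocol 9.9 nor SAP section 9 mentions the pooling.

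**Working it through.** **1. Reproduce the plan's figure.** Protocol Table 6 uses 10,000 children, one-month censoring after doses 1 and 2, and the full window r (in years) after doses 3 and 4:

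PY = 10,000 × [2 × min(r, 1/12) + 2r].

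- 12 months: 10,000 × (2/12 + 2) = 21,666.67.
- 6 weeks: 10,000 × (2/12 + 12/52) = 3,974.36.

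Both match. The 12-month row therefore takes 12 of its 26 months per child from the virtual dose-4 window.

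**2. Last first visit (V1).** SAP cap minus 44 months: 7 August 2018 (Kombewa), 27 August 2018 (Kintampo), 19 November 2018 (Navrongo).

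**3. Earliest virtual dose 4 at Navrongo.** I read SAP 6.9.3.3 ("Navrongo: subjects entered directly under protocol amendment 4 (25 September 2017")) as first entry.

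- Nominal: 25 September 2017 + 8 weeks + 18 months − 7 days = 13 May 2019.
- 6-12 weeks group at its early limits: first DTP 10 days before consent (15 September 2017) + 8 weeks + 18 months − 2 weeks − 7 days = 19 April 2019.
- Catch-up group at its early limits: two visit intervals of 25 days, + 18 months − 2 weeks − 7 days = 23 April 2019.

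All fall after 31 March 2019. This step needs no accrual assumption.

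**4. Post-introduction shares.** Assumptions: V1 spread uniformly from first to last; first V1 at Kombewa 25 January 2016 and at Kintampo 7 February 2016 (the SAP's Amendment 3 cut-offs minus 24 months); introduction on 31 March or 1 January 2019; no censoring for vaccination, death or loss, so shares lean high.

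Example, Kombewa, 12 months after dose 4, cut 31 March 2019. V1 spans 925 days. Dose 4 (V1 + 20 months − 7 days) runs from about 18 September 2017 to 31 March 2020. Children with dose 4 in the last 366 days contribute only post-introduction time; those in the preceding 365 days contribute half on average. Share = (366 + 0.5 × 365)/925 = 59%. With a 1 January cut: (455 + 182.5)/925 = 69%.

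| Window | Kombewa/Kintampo | Navrongo |
|---|---|---|
| Primary schedule, 2 or 6 weeks | 0% | 0-3% |
| Primary schedule, 12 months (meningitis) | 4-11% | 23-40% |
| D3 to D3+1Y (main malaria analysis) | 5-13% | 27-46% |
| Secondary schedule, 12 months (meningitis) | 30-38% | 59-67% |
| Dose 4 + 12 months | 59-71% | 100% |
| D1 to D4+2Y (Month 44) | 47-55% | 74-81% |

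For D3 to D4+1Y (Month 32), the equal-weight mean over the three sites is 44% (31 March) or 53% (1 January); for D3 to D3+1Y it is 13% or 23%.

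Sensitivity: front- or back-loaded accrual moves the Kombewa/Kintampo dose-4 12-month share to roughly 36-90%. If Navrongo's introduction was 30 June 2019, 92-99% of its dose-4 person-time is post-introduction (2-week to 12-month windows); if 30 September 2019, 70-94%.

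**5. Illustrative dilution of an indirect effect.** If a share p of baseline time already carries an effect d, the apparent effect is 1 − (1 − d)/(1 − p × d). With d = 20% (illustrative; not in the documents):

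- p = 13%: 1 − 0.80/0.974 = 18%.
- p = 23%: 1 − 0.80/0.954 = 16%.
- p = 60%: 1 − 0.80/0.88 = 9%.

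**6. Precision after a split.** With equal site weights, the 12-month row falls from 21,667 PY to about 13,100 (31 March) or 11,400 (1 January). For 5 events the rate per 100,000 PY and exact interval change from 23.1 [7.5, 53.9] to 38.3 [12.4, 89.3] or 44.0 [14.3, 102.7].

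**The case against.** **The overlap is deliberate.** The protocol foresees it, follows ineligible and declining children on, and concludes AS for vaccinated ones; the 44 months mirror EPI-MAL-003. One can say that for AS the boundary is set child by child. This justifies continuing follow-up. It does not justify reporting the later time, unsplit, under an objective worded as before implementation when EHS stops at the cluster date. SAP Amendment 2 added a child's own RTS,S/AS01E date to the last-contact rule, but nothing at site level.

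**A clean early rate exists.** The interim analysis has a cut-off of 5 October 2018 and last contact no later than Visit 5 (SAP 8.2.1). That does give pre-introduction AS rates, but only up to Visit 5, not for dose 4, Month 32 or Month 44.

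**The main analyses are less affected.** This stands. Primary-schedule rates are reported separately, the short AESI windows are almost wholly pre-introduction, and D3 to D3+1Y is mostly so at Kombewa and Kintampo.

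**Little mechanism outside malaria.** This stands in part. No document gives a reason why other children's vaccination would change an unvaccinated child's risk of most AESI. For those endpoints the issue is calendar period and who remains, and many will have remained because of age rather than refusal.

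**The comparison sits elsewhere.** SAP 6.11.1 and section 9 place the before/after analysis in EPI-MAL-003, whose plan is not available here and may split the data itself. That limits what can be said about bias in vaccine effects, but does not alter what EPI-MAL-002 will report against its own objective.

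**Dates are uncertain.** Protocol 9.9 allows the EPI-MAL-003 start to vary by country, and no site date is given. This also stands.

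**Conclusion.** The mismatch is real and no other section corrects it: the objective is incidence prior to implementation, EHS is closed at that point, and AS person-time is neither stopped nor split there. It affects the dose-4 and secondary-schedule rates and the Month 32 and Month 44 analyses, and at Navrongo also D3 to D3+1Y, with the shares tabulated above. Those rest on uniform accrual, assumed 2016 start dates, a Q1 2019 introduction and no censoring for vaccination, death or loss.

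Three stronger readings are tempting and not supported:

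- That the co-primary baseline as a whole is largely post-implementation. Primary-schedule AESI rates with 2- to 6-week windows are 0-3% post-introduction at most.
- That Navrongo certainly has no pre-introduction dose-4 time. This follows from the protocol's single Q1 2019 date, which may not be the site's own.
- That planned indirect effects will be roughly halved. The fall from 20% to 9% needs a 60% share, which fits late windows only. At the main malaria window's 13-23% it would be 16-18%, the effect size is illustrative, and the EPI-MAL-003 plan has not been seen.

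**What to change.** In SAP 6.9.3.2 (Table 2) and 6.11.2 (Table 3), split events and person-time at each site's RTS,S/AS01E introduction date. Report the pre-introduction rate as the one answering the objective. Give the all-follow-up rate beside it, labelled as including post-introduction time in unvaccinated children. Once Navrongo's actual introduction date is confirmed, state how much of its dose-4 person-time, if any, precedes it.

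This requires SAP wording, the site dates and one stratification of person-time already collected; no new data collection is needed. The price is wider intervals for the late-window pre-introduction rates, as in step 6, with the pooled rate still available. A before/after period term in the Poisson models is optional: those models use study-entry covariates, so it would need split records.

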### 7.3. Handling missing data

*For incidence rate computation, the missed visits will be considered as:*

- for the AS 5-17 months group*  
*If the three first home-visits planned according to the schedule are missing, the first home-visit will be imputed as:*
  - AS 5-17 months first DTP: Date of birth + 6 months*
  - AS 5-17 months catch-up: Date of ICF*
  - for the AS 6-12 weeks group: no imputation of missed visits as DTP vaccination dates will be considered for the computation of the follow-up.*

*Of note, the number of missed home-visits (without imputation) will be displayed on the flowchart section of the study report.*

### 7.4. Number of decimals

The following decimal description will be used for the analyses.

Parameters	Number of decimal digits
% of count, including LL & UL of CI	1 (except for 100% in which case no decimal will be displayed)
p-value	3
Minimum, maximum, range, Q1, Q3	Number of decimals in the raw data
Mean, median	Number of decimals in the raw data +1
SD	Number of decimals in the raw data +2

LL = Lower Limit    UL = Upper Limit    CI = Confidence Interval

SD = Standard deviation

